### **8.4. Injection Site Assessments**

Injection site assessments will be performed immediately (+10 minute) and 1 hour ( $\pm 15$  minutes) after receiving each dose of the IMP at visits 2, 3, and 4. The injection sites will be assessed for erythema, induration, and ecchymosis. More details are in Section 7.9 of the study protocol.

Injection-site reactions should be recorded as adverse events. Injection-site related adverse events will be summary as indicated in Section 8.3.

### **8.5. Hypersensitivity/Anaphylaxis**

Patients will be assessed for suspected anaphylaxis/hypersensitivity reactions during and after administration of the IMP at visits 2, 3, and 4. Data will be summarized using descriptive statistics.

The number of patients with suspected anaphylaxis/hypersensitivity reactions and number of suspected anaphylaxis/hypersensitivity reactions per patient will be summarized using descriptive statistics.

The relative time of suspected event will be calculated as date/time of suspected event - date/time of most current IMP administration and summarized using descriptive statistics. If a patient has more than one suspected anaphylaxis reactions, the earliest time will be used for the calculation.

Data will be listed.

### **8.6. Electronic Columbia Suicide Severity Rating Scale**

The eC-SSRS ‘Baseline/Screening’ version will be completed at visit 1, and the eC-SSRS ‘Since Last Visit’ version will be completed at all other visits (visits 2, 3, 4, and 5), including unscheduled visits. Any positive findings on the eC-SSRS ‘Since Last Visit’ version require evaluation by a physician or doctoral-level psychologist.

Data for patients with positive findings (having suicidal ideation or suicidal behavior) will be listed.

### **8.7. Deaths**

If any patient dies during the study, all relevant information will be discussed in the patient narrative included in the clinical study report.

### **8.8. Clinical Laboratory Tests**

Clinical laboratory tests (serum chemistry, hematology, coagulation, and urinalysis; see protocol Appendix K for the list) will be performed at all study visits using the central laboratory. All clinical laboratory test results outside of the reference range will be judged by the investigator as belonging to one of the following categories:

- abnormal and not clinically significant
- abnormal and clinically significant

A laboratory test result that is judged by the investigator as clinically significant will be recorded on the source documentation and the CRF as an adverse event, and monitored as described in Section 7.1.2 of the protocol.

Laboratory test results will be presented in standard international (SI) units in summaries. Laboratory values and changes from baseline to each visit in the double-blind treatment period and Last Assessment (see Section 4.4) will be summarized using descriptive statistics. Shifts (below [low], within [normal], and above [high] the normal range) from baseline to each visit in the double-blind treatment period and the Last Assessment will be summarized using patient

counts. Baseline is defined as the last observed data before the administration of the first dose of the IMP (also see Section 4.2).

The potentially clinically significant abnormal values will be derived using criteria specified in Table 2 based on all postbaseline values (including scheduled, unscheduled, and withdrawal visits). The overall incidence of potentially clinically significant abnormal values will be summarized for laboratory variables using descriptive statistics by treatment group. Listings for patients who have potentially clinically significant abnormal laboratory data will be presented.

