# APPENDIX I. GUIDANCE ON SAFETY MONITORING

# **Guidance on Monitoring Patients with Elevated Liver Function Tests**

Liver enzymes (alanine aminotransferase [ALT], aspartate aminotransferase [AST], gamma-glutamyl transpeptidase [GGT], and alkaline phosphatase [ALP]), as well as total, direct, and indirect bilirubin, will be measured at each study visit.

In any case of elevated ALT or AST to a level exceeding  $\ge 2 \times$  the upper limit of normal (ULN) (including subjects whose baseline ALT or AST levels are  $\ge 2 \times$  and  $\le 3 \times$  the ULN, who may be enrolled in the study), a thorough medical history and physical examination with a focus on liver disease should be undertaken. In addition, the subject should be instructed to refrain from alcoholic beverages.

In case of symptoms compatible with drug-induced liver injury during the study, subjects will be instructed to return to the study center for an unscheduled visit or to go to the emergency room to measure liver enzymes as soon as possible. Solitary elevations of total, direct, or indirect bilirubin not accompanied by elevations of ALT or AST should be managed according to the discretion of the treating physician.

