#### Elevation of Either ALT or AST to ≥3× ULN

Confirmation is required prior to study drug discontinuation in cases of elevation of either ALT or AST  $\ge 3 \times$  ULN. (Note: In cases of elevation of ALT or AST  $\ge 8 \times$  the ULN, no confirmation is required prior to study drug discontinuation, but the assessments below should be performed.) The following procedures should be followed:

- The day in which the abnormal value is received from the laboratory will be considered as day 0.
- The investigator should repeat the test for confirmation purposes (this may be performed in a local laboratory along with complete blood count [CBC] and differential to assess for eosinophilia; in general, in case a blood sample is sent to a local laboratory, the following assessments [and reference ranges] are mandatory: ALT [serum glutamic pyruvic transaminase], AST [serum glutamic oxaloacetic transaminase], ALP, bilirubin [total, direct, and indirect], CBC [with differential for eosinophil count, separate tube], and international normalized ratio (INR) [separate tube; not to be sent in a confirmatory test]). The investigator should also question the subject regarding symptoms.

<sup>1 Thorough medical history with a focus on liver disease: personal or family history of liver disease; personal history of a systemic disease with potential liver involvement; exposure to alcohol, medications (prescription or over the counter), herbal preparations, dietary supplements, recreational drugs, special diets, or environmental chemical agents; potential exposure to infectious agents (eg, travel to developing countries, history of potential exposure to blood or blood products, high-risk sexual relations); and any additional information deemed relevant by the investigator. Physical examination, including signs of chronic liver disease.

The abnormality will be regarded as confirmed in each of the following scenarios:

- The baseline value was within the normal range and ALT or AST is still  $\ge 3 \times$  the ULN.
- The baseline value was above the ULN and ALT or AST is  $>2\times$  the baseline value.

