**Table 2: Criteria for Potentially Clinically Significant Laboratory Values**

Test	Criterion value
Serum chemistry	
ALT	≥3x ULN
AST	≥3x ULN
ALP	≥3x ULN
GGT	≥3x ULN
LDH	≥3x ULN
BUN	≥10.71 mmol/L
Creatinine	≥177 μmol/L
Bilirubin (total)	≥34.2 μmol/L
Hematology	
Hematocrit	Men <0.37 L/L
	Women <0.32 L/L
Hemoglobin	Men ≤115 g/L
	Women ≤95 g/L
WBC counts	≤3 x 10  /L ≥20 x 10  /L
Eosinophils	≥10%
ANC	≤1 x 10  /L
Platelet counts	≤75 x 10  /L ≥700 x 10  /L
Urinalysis	
HGB	≥2 unit increase from baseline
Glucose	≥2 unit increase from baseline
Ketones	≥2 unit increase from baseline
Total protein	≥2 unit increase from baseline

ALP=alkaline phosphatase; ALT=alanine aminotransferase; ANC=absolute neutrophil count AST=aspartate aminotransferase; BUN=blood urea nitrogen; GGT=gamma- glutamyl transpeptidase; HGB=hemoglobin; LDH=lactate dehydrogenase; RBC=red blood cell; ULN=upper limit of normal range; WBC=white blood cell

Pregnancy tests will be performed for all women of childbearing potential. Test results will be listed.

Current menstruating status (yes or no) will be collected at all female patients. The data will be listed.

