## **8.10. Vital Signs**

Vital signs (pulse, systolic and diastolic blood pressure, and body temperature) will be measured visit 1 through visit 5. Weight will be measured at all study visits. Any vital sign value that is judged by the investigator as a clinically significant change (worsening) from a baseline value will be considered an adverse event, recorded on the source documentation and transcribed onto the CRF, and monitored as described in Section 7.1.2 of the protocol.

Vital signs (including weight) values and changes from baseline to each visit in the double-blind treatment period and the Last Assessment (see Section 4.4) will be summarized using descriptive statistics. The incidence of potentially clinically significant abnormal values will be summarized for selected vital signs using descriptive statistics. Baseline is defined as the last observed data before the administration of the first dose of the IMP (also see Section 4.2).

Table 3 specifies the criteria for identifying vital signs as potentially clinically significant abnormal values. Note that in order to qualify as potentially clinically significant abnormal, a value needs to meet both criteria below ie, have a value beyond the criterion value and a change of at least the magnitude specified in the change relative to baseline column. The potentially clinically significant abnormal vital signs values will include all postbaseline values (including scheduled, unscheduled, and early withdrawal visits) for the summaries.

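### SAP 8.8 counts chemistry and haematology abnormalities without regard to baseline, so patients who already met a limit before dose 1 are mixed into the by-arm incidence

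*SAP*

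**What the plan says.** SAP 8.8 states the rule in two steps. First, "The potentially clinically significant abnormal values will be derived using criteria specified in Table 2", applied "based on all postbaseline values (including scheduled, unscheduled, and withdrawal visits". Second, "The overall incidence of potentially clinically significant abnormal values will be summarized for laboratory variables using descriptive statistics by treatment group". Patients with flagged values are also listed.

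In Table 2 the enzyme limits are fixed multiples of the upper limit of normal (ULN). Urea nitrogen, creatinine and total bilirubin have fixed concentrations. The haematology rows are fixed values, counts or percentages, sex-specific for haematocrit and haemoglobin. None has a baseline part. The four urinalysis rows of the same table read "≥2 unit increase from baseline".

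For vital signs, SAP 8.10 says that "in order to qualify as potentially clinically significant abnormal, a value needs to meet both criteria below", and explains that the value must "have a value beyond the criterion value and a change of at least the magnitude specified in the change relative to baseline column".

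SAP 8.8 also plans summaries of change from baseline and shift tables against the normal range. SAP 4.2 defines baseline as the last observation before the first dose.

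**The concern.** An incidence table by treatment arm is read as a count of what appeared after dosing. For chemistry and haematology, this one also counts what was there beforehand. A man whose haematocrit is 0.36 L/L at baseline and at every later visit is below the Table 2 limit for men throughout, and he enters the table as a post-treatment abnormality.

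Such patients can be enrolled. Protocol 4.2 sets no numerical laboratory limits. It excludes clinically significant disease at the investigator's discretion. For liver enzymes, Appendix I explicitly allows raised values at entry, "including subjects whose baseline ALT or AST levels are" between 2 and 3 times ULN, so the permitted range ends exactly where the Table 2 limit begins.

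At stake is the reading of a small safety table. Protocol 1.3.1 names liver enzyme elevation as a potential risk. In arms of this size, one or two patients can make a difference between arms appear or disappear.

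**Working it through.** The plan states no figure for this point, so there is nothing to reproduce. The size follows from the number of patients and some assumed inputs.

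**Inputs.** Protocol 3.2 gives 87 randomised. At 1:1 this is 87/2 = 43.5, so about 43 per arm. There are three scheduled post-baseline visits in the double-blind period (visits 3, 4 and 5). The share p of patients who meet a given limit at baseline is not in the documents; I assume 2%, 5% and 10%. Within-patient laboratory variability is not given either, so below it is the unit of measurement.

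**Weight of one patient.** 1/43 = 2.3 percentage points.

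**Chance imbalance at entry.** Let X and Y be the numbers of baseline-positive patients in the two arms, independent Binomial(43, p).

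| p (assumed) | Expected per arm, 43p | Chance that the arms differ by 2 or more |
|---|---|---|
| 2% | 0.86 | 22% |
| 5% | 2.15 | 44% |
| 10% | 4.30 | 59% |

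If these patients stay beyond the limit, the whole difference appears in the incidence table with no drug effect.

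**Two constructed examples.**

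- *Noise.* Three unchanged baseline-positive patients in one arm and one in the other, with nothing new in either. As written: 3/43 = 7.0% against 1/43 = 2.3%. Among patients not meeting the limit at baseline: 0/40 against 0/42.
- *Dilution.* Two unchanged baseline-positive patients in each arm, and three new abnormalities in one arm only. As written: 5/43 = 11.6% against 2/43 = 4.7%. Among patients not meeting the limit at baseline: 3/41 = 7.3% against 0/41.

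**What a split by baseline status can and cannot do.** Place a patient's true level k within-patient SDs beyond the limit (negative means inside it). Assume no drug effect and independent normal variation at baseline and at three visits. With q = Φ(k), the chance of being counted at least once is 1 − (1 − q)³. The part counted with a negative baseline is (1 − q) × [1 − (1 − q)³].

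| k | Counted as written | of which limit not met at baseline | of which limit met at baseline |
|---|---|---|---|
| 0.5 | 97% | 30% | 67% |
| 0 | 87.5% | 44% | 44% |
| −0.5 | 67% | 46% | 21% |
| −1 | 40% | 34% | 6% |
| −2 | 7% | 7% | 0.2% |

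The split moves most of the counts from patients truly beyond a limit and few from patients just inside it.

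**Why the other outputs do not settle it.** Take one patient at 3.0 times ULN at baseline and afterwards, and another who goes from 1.2 to 3.5 times ULN. Both are flagged under Table 2, and both are high at baseline and high afterwards in the shift table. Only the second is new. Mean changes do not identify patients. SAP 8.8 does not say that the listing shows whether a flag was present at baseline.

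**The case against.** The strongest defence is that fixed limits are a legitimate choice that the plan makes elsewhere too. The special-interest liver rule (Protocol 7.1.7, repeated in SAP 8.3), the Hy's law criteria (Protocol 7.1.5.1) and the Appendix I stopping rules all use fixed multiples with no baseline term. Protocol 9.7 foresees predefined criteria on either values or changes. This stands: a reader might infer that chemistry and haematology are the sole exception in a plan otherwise referenced to baseline, and that is not so. The narrower contrast also stands, within Table 2 itself and with Table 3.

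Three further inferences go too far.

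- *Patients near a limit at entry are counted.* They are counted only if a post-baseline value reaches the limit. If they were below it at baseline, they would still count as treatment-emergent under the fix. Their crossing probabilities do not measure this problem.
- *Raised liver enzymes at entry are expected.* Appendix I only permits them, and no document gives a number.
- *The comparison between arms is biased.* Randomisation balances entry abnormalities in expectation.

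It can also be said that changes from baseline, shifts, listings and the separate summary of special-interest events already give context. They do, but the by-arm incidence itself remains mixed.

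**Conclusion.** The point holds as a minor reporting weakness. For chemistry and haematology, SAP 8.8 with Table 2 does not distinguish abnormalities present before dose 1 from those that appear afterwards. Each unchanged baseline-positive patient adds about 2.3 percentage points to an arm's incidence. If 2% to 10% of patients meet a given limit at entry, the arms differ by two or more such patients with a chance of about 22% to 59%. Those shares are assumptions; the true number could be zero for many tests. The effect is noise and dilution in a descriptive table. It touches no efficacy result and no rule for managing patients.

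**What to change.** In SAP 8.8, present the incidence for each chemistry and haematology criterion in two parts, using the SAP 4.2 baseline:

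1. Patients who did not meet that criterion at baseline, with their number as denominator. This is the treatment-emergent incidence.
2. Patients who met it at baseline, shown separately so that any worsening stays visible.

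Say how patients without a baseline value for the test are handled, and mark baseline-positive patients in the listing. The Table 2 limits stay unchanged, and the urinalysis rows need nothing.

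Do not use the baseline-relative rule in Appendix I as a filter on this table. That rule ("The baseline value was above the ULN and ALT or AST is" more than twice the baseline value) serves to confirm an abnormality before study drug is discontinued. As a filter, a patient at 2.8 times ULN would have to exceed 2 × 2.8 = 5.6 times ULN, so a rise to 5.5 would vanish from the incidence. Appendix I also uses other baseline-dependent limits in its follow-up steps, so it supplies no single rule to borrow.

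The cost is one derived flag and a slightly smaller denominator per test; the listing stays complete. SAP 2.5.2 has the plan finalised before the double-blind database lock, so the change belongs there. If it comes later, Protocol Section 9 requires it to be disclosed in the study report.

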**Table 2: Criteria for Potentially Clinically Significant Laboratory Values**

Test	Criterion value
Serum chemistry	
ALT	≥3x ULN
AST	≥3x ULN
ALP	≥3x ULN
GGT	≥3x ULN
LDH	≥3x ULN
BUN	≥10.71 mmol/L
Creatinine	≥177 μmol/L
Bilirubin (total)	≥34.2 μmol/L
Hematology	
Hematocrit	Men <0.37 L/L
	Women <0.32 L/L
Hemoglobin	Men ≤115 g/L
	Women ≤95 g/L
WBC counts	≤3 x 10  /L ≥20 x 10  /L
Eosinophils	≥10%
ANC	≤1 x 10  /L
Platelet counts	≤75 x 10  /L ≥700 x 10  /L
Urinalysis	
HGB	≥2 unit increase from baseline
Glucose	≥2 unit increase from baseline
Ketones	≥2 unit increase from baseline
Total protein	≥2 unit increase from baseline

ALP=alkaline phosphatase; ALT=alanine aminotransferase; ANC=absolute neutrophil count AST=aspartate aminotransferase; BUN=blood urea nitrogen; GGT=gamma- glutamyl transpeptidase; HGB=hemoglobin; LDH=lactate dehydrogenase; RBC=red blood cell; ULN=upper limit of normal range; WBC=white blood cell

Pregnancy tests will be performed for all women of childbearing potential. Test results will be listed.

Current menstruating status (yes or no) will be collected at all female patients. The data will be listed.

### **8.8.1. Laboratory Values Meeting Hy’s Law Criteria**

All occurrences of possible drug-induced liver injury that meet Hy’s law criteria as defined in the Section 7.1.5.1 of the study protocol will be included in serious adverse events reporting.

## **8.9. Physical Examinations**

Physical examinations will be performed at visits 1, 2, and 5. Any physical examination finding that is judged by the investigator as a clinically significant change (worsening) compared with a baseline value will be considered an adverse event, recorded on the CRF, and monitored as described in Section 7.1.2 of the study protocol.

Abnormal physical examination findings will be listed.

Weight and height will be summarized and listed with vital signs data.

## **8.10. Vital Signs**

Vital signs (pulse, systolic and diastolic blood pressure, and body temperature) will be measured visit 1 through visit 5. Weight will be measured at all study visits. Any vital sign value that is judged by the investigator as a clinically significant change (worsening) from a baseline value will be considered an adverse event, recorded on the source documentation and transcribed onto the CRF, and monitored as described in Section 7.1.2 of the protocol.

Vital signs (including weight) values and changes from baseline to each visit in the double-blind treatment period and the Last Assessment (see Section 4.4) will be summarized using descriptive statistics. The incidence of potentially clinically significant abnormal values will be summarized for selected vital signs using descriptive statistics. Baseline is defined as the last observed data before the administration of the first dose of the IMP (also see Section 4.2).

Table 3 specifies the criteria for identifying vital signs as potentially clinically significant abnormal values. Note that in order to qualify as potentially clinically significant abnormal, a value needs to meet both criteria below ie, have a value beyond the criterion value and a change of at least the magnitude specified in the change relative to baseline column. The potentially clinically significant abnormal vital signs values will include all postbaseline values (including scheduled, unscheduled, and early withdrawal visits) for the summaries.

**Table 3: Criteria for Potentially Clinically Significant Vital Signs**

Vital Sign	Criterion value	Change relative to baseline
Pulse	≥120 bpm	Increase of ≥15 bpm
	≤50 bpm	Decrease of ≥15 bpm
Systolic blood pressure	≥180 mm Hg	Increase of ≥20 mm Hg
	≤90 mm Hg	Decrease of ≥20 mm Hg
Diastolic blood pressure	≥105 mm Hg	Increase of ≥15 mm Hg
	≤50 mm Hg	Decrease of ≥15 mm Hg
Temperature	≥38.3°C	Change of ≥1.1°C

bpm=beats per minute

Height will be measured at screening visit, and data will be listed in the vital sign listing.

### 8.11. Electrocardiography

Triplicate 12-lead ECGs will be collected at study visits. Any ECG finding that is judged by the investigator as a potentially clinically significant change (worsening) compared with a baseline value will be considered an adverse event, recorded on the source documentation and in the CRF, and monitored as described in Section 7.1.2 of the protocol.

For ECG variables, the mean of recorded results from last three measurements at a visit will be calculated. The mean results and mean changes from baseline to each visit in the double-blind treatment period and Last Assessment (see Section 4.4) will be summarized using descriptive statistics. Baseline is determined based on the last set of observed data before the administration of the first dose of the IMP.

For ECG findings, the worst value of recorded from last three findings at a visit will be used for analysis. Baseline ECG findings and shifts (normal, abnormal not clinically significant, and abnormal clinically significant) from baseline to each visit in the double-blind treatment period, overall (worst value for a patient), and the Last Assessment (worst value of recorded findings from the last visit) will be summarized using patient counts.

### 8.12. Concomitant Medications or Therapies

Concomitant medications, treatments, or procedures will be recorded throughout the study.

All concomitant medications will be coded using the WHO Drug. The incidence of concomitant medications will be summarized using descriptive statistics by therapeutic class and preferred term. Patients are counted only once in each therapeutic class category, and only once in each preferred term category. The concomitant medications will include all medications taken after administration of the first IMP.

The subset of medications or therapies will be summarized by the indication categories as indicated in Section 5.5.

